13. MONITORING OF THE STUDY

This follow-up study does not need an independent surveillance committee, however a scientific council will be set up comprising the study investigators, project leaders and CRA study coordinators, parties involved in the study, a person from the Methodological Support Unit for Research and a member of the DRCI, and will meet once a year or more frequently if necessary.

14. RIGHTS OF ACCESS TO DATA AND SOURCE DOCUMENTS

14.1. ACCESS TO DATA

The sponsor is tasked with obtaining the agreement of all the parties involved in the study in order to guarantee direct access to all study sites, source data, source documents and reports for the purposes of quality control and auditing by the sponsor.

The investigators will make available the individual documents and data strictly necessary for the follow-up, quality control and auditing of the biomedical research to persons having access to these documents in accordance with current laws and regulations (articles L.1121-3 and R.5121-13 of the Public Health Code).

14.2. SOURCE DATA

Any original document or object (medical record, result of a biological examination, report of an imaging test, video recordings) making it possible to prove the existence or accuracy of data or facts recorded in the course of the research is defined as a source document.

14.3. DATA CONFIDENTIALITY

In line with current legislation (articles L.1121-3 and R.5121-13 of the Public Health Code), persons having direct access to source data will take all necessary precautions to ensure the confidentiality of information relating to research, participating persons, particularly as regards their identity, and the results obtained. These persons, as well as the investigators themselves, shall be subject to professional secrecy.

The subjects participating in the study will be coded using an identifier. For the treated group, the identifiers will correspond to those of the OTBB2 protocol, i.e. the number of the order of inclusion in OTBB2 (from 1 to 18) followed by the 1st letter of the surname and 1st letter of the first name of the patient. For the control group, the identifiers will correspond to the number of the order of inclusion in OT2suite (starting from 19) followed by the 1st letter of the surname and 1st letter of the first name of the patient.

The investigator will ensure that the anonymity of each person participating in the study is guaranteed. No information allowing the identification of persons will be communicated to third parties other than those authorised by regulatory requirements to hold this information (and who are bound by the obligation of professional secrecy).

During or at the end of the biomedical research, the data collected concerning the participating persons and transmitted to the sponsor by the investigators (or any other specialised associates) shall be anonymised. They must not in any case allow the names or addresses of the persons concerned to appear in uncoded form.

The sponsor will ensure that the legal representative of each person participating in the research has given his/her consent in writing for access to the individual data about the participant that is strictly necessary for quality control of the study.

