3.2. RESEARCH HYPOTHESES AND EXPECTED RESULTS

We have presented the very promising results of the OTBB2 study to ANSM and EMA and both agencies have strongly recommended that we collect long-term data on these patients treated before the age of 6 months.

The OTBB2 study has made it possible to show the major effects of OT on infants with PWS: on the global clinical status of the patient, eating behaviour, social skills, cerebral connectivity and circulating levels of ghrelin.

These early effects of the administration of oxytocin persist for 3 weeks after the last administration and clinical observations of the children monitored at the centre of reference in Toulouse support a long-term effect. The 18 treated children appear to have better social skills, better psychomotor development and earlier establishment of the prerequisites for communication compared with the children with PWS who were not treated. These observations are consistent with the results reported in Magel2 mice which demonstrate that early administration of OT normalises learning, memory and social skills in the adult mice. Moreover, functional modifications have been observed after treatment with oxytocin in these infants.

In accordance with the request of the agencies, we hope to re-evaluate the 18 children treated in the OTBB2 protocol and compare them to a control group of children with PWS who have never been treated with OT. The comparison will focus on communication skills, adaptive behaviour, global behaviour, orality and eating behaviour, global development, evolution of height and weight and clinical parameters, oculometric skills, cerebral activity and circulating rates of peptides implicated in eating behaviour.

The control group will consist of 18 children with PWS aged between 3 and 4 years, age-matched to the experimental group, seen at the reference centre for evaluation and/or routine monitoring.

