department of CHU de Toulouse, and in particular with [name] who began using this test as part of the routine evaluation and care of her patients. It therefore seems relevant to use the most recent version of this scale. [name] believes that there is no problem using this test at the age of 4 years, even if the upper age limit is 42 months, given that these children have a developmental delay. In order to rate the competences of the child in detail and make qualitative observations, the application of the BSID-III scale will be filmed. The use of video media for rating this test is standard practice.

- o The assessment of eating behaviour, comprising:
 - a questionnaire on eating behaviour (cf. Appendix 4) is designed and used in clinical routine by the psychologist of the PWS Reference Centre in Toulouse. Indeed, no validated scale currently takes into account the eating behaviour problems encountered specifically in children with PWS, particularly at this age. It is completed during the interview with the parents.
 - a filmed assessment of eating behaviour during a meal.
- o The assessment of orality, comprising:
 - a recording of the voice
 - a videofluoroscopy of swallowing, which represents the "gold standard" for the objective assessment of swallowing problems. It will be carried out and interpreted by the speech and language pathologist of the Reference Centre who carries these out routinely. This is a video radioscopy, the recorded images of which can be reviewed and discussed after the examination, by another expert if need be. The contrast medium used for the radioscopy of the swallowing process is Micropaque®, produced by Laboratoire Guerbet (cf. SPC, appendix 5). It is an oral suspension. In the context of the trial, each child will receive 10 ml of Micropaque® diluted in 20 ml of apple juice.
- The cerebral activity, studied by BOLD effect in functional MRI (carried out at INSERM U825 in Baudot ward, Purpan Hospital under the responsibility of [name], the head of this unit). Two types of acquisition will be carried out: a morphological MRI and a resting-state functional MRI (rs-fMRI). No injection of contrast medium will be administered to the subjects during this examination. The examination will last approximately 20 minutes. This examination has already been carried out during the OTBB2 study on the 18 infants with PWS.

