10.8. COLLECTION OF BIOLOGICAL SAMPLES

A plasma bank will be set up in order to additionally measure hormonal levels of ghrelin and certain peptides and neuropeptides involved in regulation of the appetite (leptin, cortisol, insulin, GLP-1, PYY, pancreatic polypeptide, orexin A, αMSH).

During the fasting blood test carried out for the normal follow-up of the patient, an additional EDTA tube of 5 ml will therefore be taken. The tubes will be centrifuged, the plasma collected and aliquoted then stored at -80°C before measurement. The samples will be coded using a code including the acronym of the study (OT2suite) and the identifying number of the patient specific to the research (cf. 14.3).

The plasma bank will be kept at -80°C at the Biological Resources Centre (CRB) of CHU de Toulouse under the responsibility of the principal investigator, [name]. At the end of the study, the collection will be kept for 10 years in order to be able at a later date to make hormonal level measurements not accessible at the time of the study.

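### The only subject identifier the protocol describes reveals the group (1 to 18 treated, 19 and above control), and it goes on the plasma tubes; no neutral code is described for MRI, eye-tracking files or recordings

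*Protocol*

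**What the plan says.** Section 14.3 (Data confidentiality) sets the coding rule, with a single identifier per child. Children who had oxytocin keep their earlier number: "the identifiers will correspond to those of the OTBB2 protocol, i.e. the number of the order of inclusion in OTBB2 (from 1 to 18". Controls are numbered on from there, by "the number of the order of inclusion in OT2suite (starting from 19". In both groups two initials follow the number.

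Section 10.8 (Collection of biological samples) carries the rule to the laboratory. The tubes bear a "code including the acronym of the study (OT2suite) and the identifying number of the patient specific to the research (cf. 14.3". Section 15.4 (Data management) has coded subject identification on the case report form.

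For other material read after the visit, no labelling rule is given. Section 9.2 says that "the application of the BSID-III scale will be filmed", and it also provides for a meal film, a voice recording, videofluoroscopy, resting-state fMRI and eye-tracking. Section 12.2 leaves the MRI analysis to the MRI team, by the OTBB2 method. Nowhere does the protocol describe a second code, relabelling or masked reading for OT2SUITE.

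Section 3.2 records what the team already expects: "The 18 treated children appear to have better social skills, better psychomotor development and earlier establishment of the prerequisites for communication", by comparison with untreated children.

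**The concern.** The study is open and non-randomised, and its primary outcome is a parent interview. Expectation can be kept out only of measurements whose reader has no other way of knowing the exposure: assays, scan processing and offline handling of eye-tracking files. For these, the label decides whether the reading is masked, and the label as fixed states the group.

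MRI is the clearest case because it involves judgement about which scans to keep. In OTBB2, according to the Figure 4 legend in Appendix I, 7 of the 17 infants scanned twice were discarded for head motion or field inhomogeneity, which left 10. If losses are similar here, exclusions made with the group in view could shape the comparison.

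**Working it through.** **Step 1. Does the number alone fix the group?**

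Inputs, from section 14.3 and the planned 18 + 18 children:

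- treated numbers: a subset of {1, …, 18};
- control numbers: 19, 20, …, up to 36 if 18 controls enrol.

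The two sets have no number in common. The rule that a number of 18 or less means treated classifies 18 + 18 = 36 of 36 children correctly. It still works if fewer than 18 treated children enrol, because control numbering starts at 19 regardless.

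The treated numbers should also show the OTBB2 step. Appendix I says each of the three steps took six consecutive infants, so 1–6, 7–12 and 13–18 should correspond to steps 1, 2 and 3.

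**Step 2. Where does the identifier go?**

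| Material | Label stated? | Source |
|---|---|---|
| Plasma tubes | Yes, the 14.3 identifier | 10.8 |
| Case report form | Yes, coded identification | 15.4 |
| MRI and eye-tracking files | No | 9.2, 10.5, 12.2 |
| BSID-III film, meal film, voice, videofluoroscopy | No | 9.2, 10.5 |

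For the last two rows, use of the 14.3 number is an inference from its being the only subject code described.

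**Step 3. Where would a neutral code change what the reader knows?**

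- *Laboratory, MRI team, offline eye-tracking work:* the reader need not know the child's history, so a neutral code can mask the group.
- *Videofluoroscopy:* carried out and interpreted by the reference centre's own speech and language pathologist (9.2), with the child present. A code does not mask it.
- *BSID-III:* administered in person by the speech therapist and psycho-motor therapist (10.5). A film of it shows a child whom centre staff may recognise, since the OTBB2 children are followed there regularly (6.1, 6.3). A code alone does not mask it.
- *Vineland-II:* completed with parents who know whether their child received oxytocin (10.5). A code does not mask it.

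**Step 4. Illustration of size, under an assumed bias.**

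The protocol's only statistical figure is the sample size. With a difference of 15, SD 15, two-sided 5% and 80% power, the t-based solution is 16.71 per group. This rounds up to the stated 17 (section 12.1).

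With 18 per group and no true effect, a reading bias of b points gives a noncentrality of b / (15 × √(2/18)) = b / 5 on 34 degrees of freedom:

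| Assumed bias | b (points) | b / 5 | Two-sided rejection rate |
|---|---|---|---|
| none | 0 | 0 | 5% |
| 0.2 SD | 3 | 0.6 | 9% |
| 0.5 SD | 7.5 | 1.5 | 31% |

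The bias values are not in the document. The points are on the Vineland-II scale; for another outcome only the SD units carry over.

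**The case against.** The best case against the point has four parts.

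1. *Labelling of films and scans is not stated.* A reader might infer that every film and scan announces the group. The protocol documents the revealing label only for plasma tubes and, as coded identification, for the case report form. A separate reading code could sit in the data management plan or the operating procedures, which are not shown. This stands, so the point is limited to material that is in fact labelled with the 14.3 identifier.

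2. *The number is often not what unblinds the reader.* A reader might infer that relabelling would mask all recorded outcomes at no cost. Step 3 shows otherwise: where centre staff do the examination or know the child, masking needs raters from outside. This stands too.

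3. *OTBB2 is not a direct precedent.* A reader might infer that OT2SUITE drops a safeguard its predecessor had. In Appendix I the blind scoring covered two scales on videos taken before and after treatment, in children who were all treated. It masked the time point, not the group, and did not depend on subject numbers. It shows that the centre can arrange masked rating, and no more.

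4. *Little is at stake.* No blinding is promised, so nothing is contradicted. Section 12.2 calls the analyses primarily exploratory, the outcomes concerned are secondary, and keeping OTBB2 numbers gives direct linkage to the earlier data. Assays leave less room for expectation than rated films. This limits the weight of the point but does not justify a code that states the group when a neutral one is available.

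**Conclusion.** The point holds in a limited form. As written, the identifier gives the group for 36 of 36 planned children. It is on the plasma tubes by explicit cross-reference, and no alternative code is described for MRI, eye-tracking files or recordings. This is a rule fixed badly, not an internal contradiction.

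The bias cannot be quantified from the document. A reader might take 9% to 31% as the size of the defect. It is at most an illustration: it rests on an assumed bias of 0.2 to 0.5 SD, and its point values belong to the Vineland-II outcome, which a new code cannot mask. Nothing in the document supports applying that bias to peptide assays or resting-state fMRI.

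The benefit of a change is confined to secondary, mainly exploratory outcomes, and depends on the laboratory, the MRI team and those processing eye-tracking files having no other source of group information. The change is worth making because it is nearly free and cannot be made retrospectively for material already read with the group visible.

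**What to change.** Amend sections 14.3 and 10.8:

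- Give each child a random OT2SUITE code unrelated to group, order of inclusion or initials.
- Have the data manager hold the link list, including the OTBB2 numbers.
- Label plasma aliquots, MRI files and eye-tracking files with that code only.
- Have the laboratory and the MRI team work from the code, and decide scan exclusions before the link is opened.

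The cost is one link table and the relabelling. The small downside is that OTBB2 data are then joined through the table and no longer by number. Sample size, power and study visits are unchanged.

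The amendment should not claim to mask the Vineland-II interview, nor videofluoroscopy, BSID-III or films scored by centre staff who know the children. Masking recorded assessments of that kind would need outside raters, which is a separate decision and not part of this fix.

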15. QUALITY CONTROL AND ASSURANCE

15.1. INSTRUCTIONS FOR COLLECTING DATA

All information required by the protocol must be entered into the case report forms and an explanation must be given for any missing information. The data must be collected as it is obtained and transcribed into these case report forms neatly and legibly.

Incorrect data removed from the case report forms will be clearly struck out and the new data will be copied next to the struck out information, together with the initials, date and possibly an explanation by the investigator or authorised person who has made the correction.

15.2. STUDY FOLLOW-UP

The follow-up of the study will be carried out by a clinical research associate. He/she will be tasked by the coordinating investigator with:

- the logistics and monitoring of the study,
- drawing up reports concerning its progress,
- checking the updating of the case report forms (request for additional information, corrections, etc.),
- sending samples,
- transmission of SAEs to the sponsor.

He/she will work in accordance with the standardised operating procedures, in collaboration with the clinical research associate delegated by the sponsor.

15.3. QUALITY CONTROL

A clinical research associate authorised by the sponsor will regularly visit the investigation centre, during the set-up of the research, once or more during the study according to the rate of inclusions, and at the end of the study. During these visits the following elements will be reviewed:

- informed consent,
- > compliance with the study protocol and the procedures defined therein,
- > quality of the data collected in the case report form: accuracy, missing data, coherence of data with source documents (medical files, appointment calendars, originals of laboratory results, etc.),

Every visit will be the subject of a written monitoring report.

15.4. DATA MANAGEMENT

A list identifying the subjects participating in the study will be kept in the investigator's file.

The information will be collected for each subject in a standardised case report form completed by the investigator or CRA. The case report form will include the identification of the subject (coded), clinical data and study data.

The source document (existing medical file) will be kept for each subject participating in the study; observation and medical follow-up concerning the study must be recorded in the source document.

All the data from the study will be transcribed in the case report form and kept by the investigating doctors of CHU de Toulouse under the responsibility of [name]. The case report forms will be completed legibly and indelibly using a blue or black ball point pen. In case of error, the incorrect data will be struck through with a single line, so that the original information remains legible, and the correct information will be written next to it. Each correction will be explained and authenticated (dated and signed or initialled by the investigator). The principal investigator will sign each case report form to certify his/her agreement with the data included therein. The study data is then entered into a file created using Excel software by simple data entry with rereading by the study CRAs.

The data is saved automatically after the entry of new data and is kept for 15 years after the end of the study. The data is validated in accordance with the data management plan defined jointly between the coordinating investigator and the Centre of Methodology and Data Management (methodologist, data manager and statistician).

The process of freezing/unfreezing the data is carried out in accordance with the procedure set up in the Centre of Methodology and Data Management (freezing of raw data in XML format and in the form of an SAS table).

15.5. AUDIT AND INSPECTION

An audit may be carried out at any time by persons authorised by the sponsor and independent of the study managers. The aim of the audit is to ensure the quality of the research, the validity of its results and compliance with the law and current regulations.

The investigators undertake to conform with the sponsor's requirements and with the competent authority with regard to an audit or inspection of the study.

The audit may apply to all stages of the research, from development of the protocol to the publication of results and classification of the data used or produced in the context of the research.

16. ETHICAL AND REGULATORY CONSIDERATIONS

The sponsor and the investigator(s) undertake that this research shall be carried out in accordance with law number 2004-806 of 9 August 2004, and in accordance with Good Clinical Practice (I.C.H. version 4 of 1 May 1996 and decision of 24 November 2006) and the Helsinki Declaration (cf. full version http://www.wma.net).

The study is conducted in accordance with this protocol. Except in urgent situations requiring the implementation of precise therapeutic actions, the investigator(s) undertake(s) to respect all points of the protocol, in particular regarding the collection of consent and notification and the follow-up of serious adverse events.

This study received the favourable decision of the Comité de Protection des Personnes (CPP) Sud-Ouest et Outre-Mer I [Ethics Committee for South-West France and Overseas] on 21/11/2016 and the authorisation of ANSM on 22/12/2016.

CHU de Toulouse, the sponsor for this study, has taken out an civil liability insurance policy with the company GERLING France in accordance with the provisions of article L1121-10 of the Public Health Code.

The data recorded in this study will be processed electronically at CHU de Toulouse subject to the law no. 78-17 of 6 January 1978 relating to information technology, files and civil liberties as amended by law 2004-801 of 6 August 2004.

This study falls within the framework of "Reference Methodology" (MR-001) under the provisions of article 54 paragraph 5 of the amended law of 6 January 1978 relating to information, files and liberties. This change has been approved by the decision of 5 January 2006. CHU de Toulouse has signed a commitment to comply with this "Reference Methodology".

- This study is registered in the European RCB database under registration number 2016-A01348-43 in accordance with article L1121.15 of the Public Health Code.
- This study is registered on the website http://clinicaltrials.gov/.
- The collection of biological samples carried out in the context of this study was declared to ANSM at the same time as the request for authorisation of the study. After the study, the conservation of the collection of biological samples will be declared to the minister in charge of research and the Director of the Regional Health Authority (and submitted to the CPP for an opinion if there is a change in the purpose of the study).

PROTOCOL AMENDMENT

Any substantial amendment, i.e. any amendment likely to have a significant impact on the protection of persons, on the conditions of validity and on the results of the research, on the interpretation of the scientific documents supporting the implementation of the study or on the methods of conducting the study, shall be the subject of a written amendment which is submitted to the sponsor; the latter must, prior to its implementation, obtain a favourable decision from the CPP and authorisation from ANSM.

Non-substantial amendments, i.e. those which do not have a significant impact on any aspect of the research, are communicated to the CPP for information.

All amendments are validated by the sponsor, and by all the parties involved in the study concerned by the amendment, prior to submission to the CPP and ANSM. This validation may require a meeting of the CS and/or CIS.

All amendments to the protocol must be brought to the notice of all the investigators participating in the study. The investigators undertake to respect the content of these.

Any amendment which alters the care of patients or the benefits, risks and burdens of the study shall be the subject of a new information note and a new consent form, the collection of which follows the same procedure as that described above.

